7.3 Lost to Follow-Up

A participant will be considered lost to follow-up if he or she repeatedly fails to return for scheduled visits and is unable to be contacted by the study site.

The following actions will be taken if a participant fails to return to the clinic for a required study visit:

- The site will attempt to contact the participant and reschedule the missed visit as soon as possible, counsel the participant on the importance of maintaining the assigned visit schedule and ascertain if the participant wants to or should continue in the study.
- Before a participant is deemed “lost to follow-up”, the Investigator or designee will make every effort to regain contact with the participant: 1) where possible, make 3 telephone calls; 2) if necessary, send a certified letter (or an equivalent local method) to the participant’s last known mailing address, and 3) if a participant has given the appropriate consent, contact the participant’s general practitioner or caretaker (where allowed by local regulations) for information. These contact attempts will be documented in the participant’s medical record.
- If the participant continues to be unreachable, he/she will be deemed as “lost to follow-up”.

8 Study Assessments and Procedures

- Study assessments and procedures and their timing are summarized in the Schedule of Assessments (Section 1.3).
- No protocol waivers or exemptions are allowed.
- Immediate safety concerns are discussed with the Sponsor immediately upon occurrence or awareness to determine if the participant should continue or discontinue study intervention.
- Adherence to the study design requirements, including those specified in the Schedule of Assessments, is essential and required for study conduct.
- All screening evaluations will be completed and reviewed to confirm that potential participants meet all eligibility criteria. The Investigator will maintain a screening log to record details of all participants screened, to confirm eligibility, and if applicable, record reasons for screening failure.

- Prior to performing any study assessments that are not part of the participant's routine medical care, the Investigator will obtain written informed consent as specified in [Appendix 2](#).
- Procedures conducted as part of the participant's routine medical care (e.g., blood count) and obtained before signing of the ICF may be used for screening or baseline purposes provided the procedures met the protocol-specified criteria and were performed within the time frame defined in the Schedule of Assessments.
- Demographic data collected at Screening will include, at minimum, age, sex, race (collected only where allowed by local law/regulations), and ethnicity.
- No more than 50 mL of blood may be drawn in a 24-hour period, and no more than 150 mL of blood in a 4-week period.
- Where allowed by local law/regulations, samples collected during this clinical study may be transferred to a biobank and used for future research outside the clinical protocol when additional consent for this purpose is given. Transfer to the biobank will be documented and any testing of coded biobank samples will **not** be reported in the CSR.
- The long-term storage of samples after study completion for future research may be performed with all sample types collected in the study (e.g., PK, **CCI** [REDACTED]
CCI [REDACTED] or **CCI** [REDACTED] if the participant consents to optional future medical research.

8.1 Efficacy Assessments and Procedures

Not applicable.

8.2 Safety Assessments and Procedures

The safety profile of the study intervention will be assessed through the recording, reporting and analysis of baseline medical conditions, AEs, physical examination findings, vital signs, electrocardiograms, and laboratory tests.

Comprehensive assessment of any potential toxicity experienced by each participant will be conducted starting when the participants give informed consent and throughout the study. The Investigator will report any AEs, whether observed by the Investigator or reported by the participant; the reporting period is specified in [Section 8.3](#).

8.2.1 Physical Examinations

- A complete physical examination will include, at a minimum, assessments of the cardiovascular, respiratory, gastrointestinal and neurological systems.
- A brief physical examination will include, at a minimum, assessments of the skin, lungs, cardiovascular system, and abdomen (liver and spleen).
- Investigators will pay special attention to clinical signs related to previous serious illnesses.

8.2.2 Vital Signs

- Blood pressure and participant's position; pulse; respiratory rate; temperature and location of measurement, weight, and height (at Baseline only) will be measured and recorded.
- Blood pressure and pulse measurements will be preceded by at least 5 minutes of rest for the participant in a quiet setting without distractions (e.g., television, cell phones) and measured with an automated device. Manual techniques will be used only if an automated device is not available.
- Vital signs will be measured in supine position.

8.2.3 Electrocardiograms

- Single 12-lead ECG will be obtained as outlined in the Schedule of Assessments (Section 1.3) using an ECG machine that automatically measures heart rate, PR, RR, QRS, QT, and QTcB or QTcF. Documentation of the QTcF is mandatory.
- 12-Lead ECGs will be recorded in a supine position following 5 minutes of rest.

8.2.4 Clinical Safety Laboratory Assessments

- Blood and urine samples will be collected for the clinical laboratory tests listed in [Appendix 5](#) at the time points listed in the Schedule of Assessments (Section 1.3). All samples will be clearly identified.
- Additional tests may be performed at any time during the study, as determined necessary by the Investigator or required by local regulations.
- The tests will be performed by Nuvisan GmbH laboratory.
- The Investigator will review each laboratory report, document this review, and record any clinically significant changes occurring during the study as an AE, unless it does **not** meet the AE definition, as specified in [Appendix 4](#). The laboratory reports will be filed with the source documents.

8.2.5 Suicidal Ideation and Behavior Risk Monitoring

Not applicable.

8.3 Adverse Events, Serious Adverse Events, and Other Safety Reporting

- The definitions of an AE and a SAE are in [Appendix 4](#).
- The Investigator and any qualified designees (e.g., Sub-Investigators) are responsible for detecting, documenting, and recording events that meet the definition of an AE or SAE. The Investigator remains responsible for following up AEs that are serious, considered related to the study intervention or study procedures, or that caused the participant to discontinue the study intervention or study, as specified in Section 8.3.2.

- Requests for follow-up will usually be made via the Sponsor or CRO-designated study team member, although in exceptional circumstances the global patient safety department may contact the Investigator directly to obtain further information or to discuss the event.
- The method of recording, evaluating, and assessing causality of AEs and SAEs and the procedures for completing and transmitting SAE reports are in [Appendix 4](#).
- All AEs and SAEs will be collected from the signing of the ICF until the Safety Follow Up Visit at the time points specified in the Schedule of Assessments (Section 1.3). Beyond this reporting period, any new unsolicited SAEs that the Investigator spontaneously reports to the Sponsor will be collected and processed.
- All SAEs will be recorded and reported to the Sponsor or designee immediately and under no circumstance will this exceed 24 hours, as indicated in [Appendix 4](#). The Investigator will submit any updated SAE data to the Sponsor within 24 hours of it being available using the same procedure that was used for the initial report.
- Investigators are not obligated to actively solicit information on AEs or SAEs after the end of study participation. However, if the Investigator learns of any SAE, including a death, at any time after a participant has been discharged from the study, and he/she considers the event to be reasonably related to the study intervention or study participation, the Investigator will promptly notify the Sponsor.

8.3.1 Method of Detecting Adverse Events and Serious Adverse Events

- At each study visit, the participant will be queried on changes in his or her condition.
- Care will be taken not to introduce bias when detecting AEs and/or SAEs. Open-ended and nonleading verbal questioning of the participant is the preferred method to inquire about AE occurrences.
- The method of recording, evaluating, and assessing causality of AEs and SAEs and the procedures for completing and transmitting SAE reports are in [Appendix 4](#).

8.3.2 Follow-up of Adverse Events and Serious Adverse Events

- After the initial AE/SAE report, the Investigator is required to proactively follow each participant at subsequent visits/contacts. All SAEs and AESIs (as defined in Section 8.3.7) will be followed until resolution, stabilization, the event is otherwise explained, or the participant is lost to follow-up (as defined in Section 7.3). Reasonable attempts to obtain this information will be made and documented. It is also the Investigator's responsibility to ensure that any necessary additional therapeutic measures and follow-up procedures are performed. Further information on follow-up procedures is in [Appendix 4](#).

8.3.3 Regulatory Reporting Requirements for Serious Adverse Events

- Prompt notification by the Investigator to the Sponsor of an SAE (particularly life-threatening and deaths) is essential so that legal obligations and ethical responsibilities towards the safety of participants and the safety of a study intervention under clinical investigation are met.
- The Sponsor has a legal responsibility to notify both the local regulatory authority and other regulatory agencies about the safety of a study intervention under clinical investigation. The Sponsor will comply with country-specific regulatory requirements relating to safety reporting to the regulatory authority, IRB/IEC, and Investigators.
- Individual Case Safety Reports will be prepared for SUSARs according to local regulatory requirements and Sponsor policy and forwarded to Investigators, as necessary.
- An Investigator who receives an Individual Case Safety Report describing a SUSAR or other specific safety information (e.g., Emerging Safety Issue Report, summary or listing of SAEs/SUSARs) from the Sponsor will review and file it in the Investigator's Site File and will notify the IRB/IEC, if appropriate according to local requirements.

8.3.4 Pregnancy

- Details of all pregnancies in female partners of male participants will be collected after the start of study intervention and until at least 3 months after the last dose of study intervention.
- If a pregnancy is reported, the Investigator will record the pregnancy information on the appropriate form and submit it to the Sponsor within 24 hours of female partner of male participant (after obtaining the necessary signed informed consent from the female partner) pregnancy.
- While pregnancy itself is not considered to be an AE or SAE, any pregnancy complication or elective termination of a pregnancy will be reported as an AE or SAE. Adverse pregnancy outcomes (e.g., spontaneous abortion, fetal death, stillbirth, congenital anomalies, ectopic pregnancy) are considered and reported as SAEs. A spontaneous abortion (occurring at < 22 weeks gestational age) or stillbirth (occurring at > 22 weeks gestational age) is always considered to be an SAE and will be reported as such.
- The participant /pregnant female partner will be followed to determine the outcome of the pregnancy. The Investigator will collect follow-up information on the participant /pregnant female partner and the neonate, and the information will be forwarded to the Sponsor. Generally, follow-up will not be required for longer than 6 to 8 weeks beyond the estimated delivery date for a healthy newborn. In case of a congenital anomaly or other illness of the newborn, follow-up will continue until the illness has resolved or there is a definite outcome of the event.
- Any poststudy pregnancy related SAE considered reasonably related to the study intervention by the Investigator will be reported to the Sponsor as specified in Section 8.3.3. While the Investigator is not obligated to actively seek this information in former study participants /pregnant female partner, he or she may learn of an SAE through spontaneous reporting.

- Any female participant who becomes pregnant while participating in the study will discontinue study intervention or be withdrawn from the study.

8.3.5 Cardiovascular and Death Events

Not applicable.

8.3.6 Disease-Related Events and/or Disease-Related Outcomes Not Qualifying as AEs or SAEs

Not applicable.

8.3.7 Adverse Events of Special Interest

For this study, AESIs include only the following:

- AEs suggestive of drug-induced liver injury including hepatic/liver failure and hepatitis (noninfectious) are considered AESIs.

AESIs will be reported to the Sponsor (or delegate) immediately manner as described in [Appendix 4](#).

8.4 Pharmacokinetics

Collection of Plasma for Pharmacokinetic Analysis

For details on PK sampling timepoints, see the Schedule of Assessments in Section 1.3, and Table 1 and Table 2.

The following PK parameters will be calculated, when appropriate, for tepotinib and **C**
CI [REDACTED]:

Symbol	Definition
AUC _{0-∞}	The AUC from time zero (dosing time) extrapolated to infinity, based on the predicted value for the concentration at t_{last} , as estimated using the linear regression from λ_z determination. $AUC_{0-∞} = AUC_{0-t_{last}} + C_{last\ pred} / \lambda_z$
AUC _{0-t_{last}}	The area under the concentration-time curve (AUC) from time zero (= dosing time) to the time of the last quantifiable concentration (t_{last}), calculated using the mixed log-linear trapezoidal rule (linear up, log down).
AUC _{0-24h}	The AUC from time zero (= dosing time) to timepoint 24 hours. Calculated using the mixed log-linear trapezoidal rule (linear up, log down).
AUC _{0-t_{last}} /Dose	The dose normalized AUC from time zero to the last sampling time (t_{last}) at which the concentration is at or above the lower limit of quantification. Normalized using the actual dose, using the formula $AUC_{0-t_{last}}/\text{Dose}$.
AUC _{0-24h} /Dose	The dose normalized AUC from time zero to timepoint 24 hours. Normalized using the actual dose, using the formula AUC_{0-24h}/Dose .
C _{max}	Maximum observed concentration.
C _{max} /Dose	The dose normalized maximum concentration. Normalized using the actual dose, and the formula C_{max}/Dose .
T _{max}	The time to reach the maximum observed concentration collected during a dosing interval (unless otherwise defined, take the 1 st occurrence in case of multiple/identical C _{max} values)
t _{1/2}	Apparent terminal half-life. $T_{1/2} = \ln(2) / \lambda_z$
λ _z	Terminal first order (elimination) rate constant. Determined from the terminal slope of the log-transformed concentration curve using linear regression on terminal data points of the curve.
CL/F (parent drug only)	The apparent total body clearance of study intervention following extravascular administration. $CL/F = \text{Dose}_{po} / AUC_{0-∞}$. Parent drug, only.
V _z /F (parent drug only)	The apparent volume of distribution during the terminal phase following extravascular administration $V_z/F = \text{Dose} / (AUC_{0-∞} \times \lambda_z)$ following single dose. Parent drug, only.
AUC _{extra%}	The AUC from time t_{last} extrapolated to infinity given as percentage of $AUC_{0-∞}$. $AUC_{extra\%} = (\text{extrapolated area}/AUC_{0-∞}) \times 100$.
	CCI [REDACTED] [REDACTED] [REDACTED]
	[REDACTED] [REDACTED] [REDACTED]

- Whole blood samples of approximately 2 mL per collection for measurement of plasma concentrations of tepotinib and its CCI CCI will be collected. Collection times are specified in the Schedule of Assessments (Section 1.3) and Table 1. The actual date and time (24-hour clock time) of each sample will be recorded to calculate actual time elapsed since the prior dose administration.
- The quantification of tepotinib and its CCI CCI in plasma will be performed using a validated assay method. Concentrations will be used to evaluate the PK of tepotinib and its metabolites.
- Remaining samples collected for analyses of tepotinib concentration may also be used to evaluate safety or efficacy aspects related to concerns arising during or after the study.
- Details on processes for collection and handling of these samples are in the Laboratory Manual. Retention time and possible analyses of samples after the end of study are specified in the respective ICF.
- PK parameters will be derived using noncompartmental methods with the validated computer program.

The exact date and time of sample collection and study intervention (24-hour clock time) must be recorded in the eCRF and will be used in the calculation of PK parameters. The accepted time deviations from planned tepotinib PK times that will not be considered a protocol violation are listed below (Table 2).

Table 2 PK Sampling Time Windows

Procedure	Time Point (Relative Time)	Window Allowance
Pharmacokinetics	Predose	- 60 min
	1 to 12 hours postdose	- 5 / + 5 min
	> 12 to 24 hours postdose	- 30 / + 30 min
	> 24 to 72 hours postdose	- 60 / + 60 min
	> 72 to 168 hours postdose	- 180 / + 180 min

Any deviation from the above-mentioned time windows requires a comment in the eCRF and may be discussed in the data review meeting.

Collection of Feces for Pharmacokinetic Analysis

In both in-house periods of the study, all feces after administration of tepotinib until discharge from the CRU (i.e., from Day 1 to Day 4, and from Day 12 to Day 15) will be collected for exploratory tepotinib pharmacokinetic analysis.

- To ensure defecation, participants will receive a mild laxative on the evenings of Day 3 and Day 14.
- The exact date and time of sample collection and study intervention (24-hour clock time) must be recorded in the eCRF.

- The cumulative amount (% of dose) of tepotinib excreted in the feces during this time will be quantified.
- Details on processes for collection and handling of these samples are in the Laboratory Manual.

CCI [REDACTED]

CCI [REDACTED]

[REDACTED]

9 Statistical Considerations

All planned analyses defined in this protocol will be described in the IAP that will be finalized before the database lock.

Changes in the conduct of the study or planned analyses, if any, will be reported in the appropriate section of the IAP and in the clinical study report.

9.1 Statistical Hypotheses

The statistical analysis of study data will be purely descriptive; no hypothesis tests will be performed. A definition of primary, secondary and CCI [REDACTED] objectives and endpoints can be found in Section 3.

9.2 Sample Size Determination

A maximum of 18 participants will be assigned to study interventions such that at least 14 evaluable participants complete the study.

Although no hypothesis tests will be performed, the sample size of the study should be sufficient to estimate the difference between dosing conditions with adequate precision.

Available information on intraparticipant variability of tepotinib PK parameters following administration of TF2 and/or TF3 under different dosing conditions, observed in studies MS200095_0044, MS200095_0038 and MS200095_0039 are presented in [Table 3](#). The intraparticipant CV is approximately between 10.4% and 18.0% for $AUC_{0-\infty}$ and $AUC_{0-t_{last}}$, and for C_{max} between 12.7% and 16.4%.

Table 3 Overview of Observed Intraparticipant Variability of Tepotinib Pharmacokinetic Parameters

Study	Comparison	N	Mixed Intraparticipant CV		
			$AUC_{0-t_{last}}$	$AUC_{0-\infty}$	C_{max}
MS200095_0044 Part A	TF3 versus TF2 (fasted)	38	15.77%	15.83%	13.94%
MS200095_0044 Part B	TF2 (fed versus fasted)	14	17.96%	17.95%	12.67%
MS200095_0044 Part C	TF3 (fed versus fasted)	12	14.93%	15.10%	16.79%
MS200095_0038	5 × 100 mg TF3 versus 2 × 250 mg TF3 (fasted)	18	15.26%	15.29%	16.37%
MS200095_0039	Tepotinib Fed + Omeprazole versus Tepotinib Fed	12	10.41%	10.93%	16.22%

CV=Coefficient of Variation, N=number of participants.

Thus, assuming an intraparticipant CV (%) of 10%, 15%, and 20% for AUC and C_{max} of tepotinib, the precision for the estimated ratio (coadministration of tepotinib and itraconazole versus tepotinib alone) to be achieved with a given number of evaluable participants is summarized in [Table 4](#). Assuming a CV of 20%, if 14 evaluable participants are included in the study and the observed ratio is exactly 1.0, then the 90% CI for the ratio will be contained with 80% probability in 0.805 to 1.242. If the observed ratio is exactly 2.0, then the corresponding limits are 1.611 to 2.484.

This precision is considered adequate to characterize the effect of multiple doses of itraconazole on the PK of tepotinib. A further increase in sample size does not substantially improve the precision. On the other hand, even with a slightly smaller number of completed participants, the precision will be markedly decreased.

Table 4 Width of the 90% CI for the Ratio of Pharmacokinetic Parameters, for Different Geometric Mean Ratios, Sample Sizes, and Within-Participant CVs

Observed Treatment Ratio	N (total)	90% Confidence Interval with 80% Tolerance Probability		
		CV = 10%	CV = 15%	CV = 20%
1.000	10	0.871-1.148	0.814-1.229	0.761-1.315
	12	0.886-1.129	0.834-1.198	0.786-1.272
	14	0.897-1.115	0.849-1.177	0.805-1.242
	16	0.905-1.105	0.861-1.161	0.820-1.220
	18	0.911-1.097	0.870-1.149	0.832-1.202
2.000	10	1.743-2.295	1.628-2.457	1.521-2.629
	12	1.772-2.257	1.669-2.397	1.573-2.543
	14	1.793-2.231	1.699-2.354	1.611-2.484
	16	1.810-2.210	1.722-2.323	1.640-2.439
	18	1.823-2.195	1.741-2.298	1.663-2.405
5.000	10	4.357-5.738	4.069-6.144	3.804-6.573
	12	4.430-5.643	4.172-5.992	3.932-6.358
	14	4.483-5.576	4.247-5.886	4.026-6.209
	16	4.524-5.526	4.305-5.807	4.099-6.098
	18	4.557-5.486	4.352-5.745	4.158-6.012

Calculation performed in R version 3.5.1.

CV=coefficient of variation.

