1.1 Synopsis

Protocol Title: Phase I, Open-label, Single-sequence, Cross-over Study of the Effect of Multiple Doses of Itraconazole on Single-dose Tepotinib Pharmacokinetics in Healthy Participants

Short Title: Tepotinib Drug-Drug Interaction Study With Itraconazole in Healthy Participants

CCI

Objectives and Endpoints:

Objectives	Endpoints	Ref #
Primary		
To investigate the effect of multiple doses of itraconazole on tepotinib PK in healthy participants	
Plasma tepotinib: $AUC_{0-\infty}$, $AUC_{0-t_{last}}$, and C_{max}	1
Secondary		
To assess the safety and tolerability of tepotinib when administered together with itraconazole in healthy participants	
Nature, occurrence, severity, and seriousness of TEAEsAbsolute values and changes in safety laboratory testsSingle 12-lead ECGs evaluated by InvestigatorVital signs assessed from time of first dose to end of study participation	2
To characterize the effect of multiple doses of itraconazole on additional tepotinib PK parameters in healthy participants	
Plasma tepotinib: CL/F, V_z/F, t_{max}, and $t_{1/2}$	3

ECG=electrocardiogram, PK=pharmacokinetics, TEAE=treatment emergent adverse events.

Overall Design: This will be a nonrandomized, open-label, single-sequence, cross-over Phase I study in healthy participants.

Brief Summary:

The purpose of this study is to assess the effect of multiple doses of itraconazole on single-dose tepotinib pharmacokinetics in healthy participants. Study details include:

[figure not shown]
- Study Duration: up to 48 days
- Treatment Duration: single dose of tepotinib on Days 1 and 12, 11 days of treatment with itraconazole (Days 8 to 18)
- Visit Frequency: residence in the Clinical Research Unit from Days -1 to 4 and Days 11 to 15, ambulatory daily visits from Days 5 to 10 and 16 to 20

Number of Participants: A maximum of 18 participants will be assigned to study interventions such that at least 14 evaluable participants complete the study.

Study Intervention Groups and Duration: 21 days of intervention period including Safety Follow Up on Day 20; single dose of tepotinib on Days 1 and 12, 11 days of treatment with itraconazole (Days 8 to 18).

Involvement of Special Committee(s): No

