9.3 Analyses Sets

The analysis sets are specified below. The final decision to exclude participants from any analysis sets will be made during a data review meeting prior to database lock.

Analysis Set	Description
Screening (SCR)	All participants, who provided informed consent, regardless of the participant's enrollment and study intervention status in the study.
Safety (SAF)	All participants, who were administered any dose of any study intervention. Analyses will consider participants as treated.
Pharmacokinetic (PK)	The PK Analysis Set is a subset of the SAF, and the PK population will include all participants: Who have completed the study without any relevant protocol deviations and factors likely to affect the comparability of PK results. With adequate study intervention compliance. With evaluable PK data, i.e., nonmissing values for primary endpoints. If participants received prohibited concomitant therapy or medicines, as specified in Section 6.8.3, they will be excluded from the PK population. All PK analyses will be based on this analysis set.

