9.4.3 Other Analyses

Analysis of Primary Endpoints

The effect of coadministration of itraconazole on tepotinib exposure will be assessed. A general linear model with a fixed effect for TREATMENT and a random effect for SUBJECT will be applied to the log-transformed PK parameters C_{max} , $AUC_{0-tlast}$ and $AUC_{0-\infty}$ based on the PK analysis set. Treatment differences on the log scale of tepotinib with itraconazole versus tepotinib alone (Day 12 versus Day 1) will be estimated for the C_{max} , $AUC_{0-tlast}$ and $AUC_{0-\infty}$ together with their 90% CIs. Point estimates and CIs will be back transformed to the original scale for presentation.

The analysis will be repeated with both SUBJECT and TREATMENT as fixed effects.

CCI [REDACTED]

[REDACTED]

CCI [REDACTED]

[REDACTED]

[REDACTED]

[REDACTED]

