16.1.3 Statistical Analysis of PK Parameter Data

Analysis of Primary Endpoints

The effect of co-administration of itraconazole on tepotinib exposure will be assessed. A general linear model with a fixed effect for TREATMENT and a random effect for SUBJECT will be applied to the log-transformed PK parameters C_{max} , $AUC_{0-tlast}$ and $AUC_{0-\infty}$ based on the PK analysis set. Treatment differences on the log scale of tepotinib with itraconazole versus tepotinib alone (Day 12 versus Day 1) will be estimated for the C_{max} , $AUC_{0-tlast}$ and $AUC_{0-\infty}$ together with their 90% CIs. Point estimates and CIs will be back transformed to the original scale for presentation.

The analysis will be repeated with both SUBJECT and TREATMENT as fixed effects.

CCI [REDACTED]

[REDACTED]

[REDACTED]

[REDACTED]

The analysis will be repeated with both SUBJECT and TREATMENT as fixed effects.

CCI [REDACTED]

[REDACTED]

[REDACTED]

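### Table 4 and the two precision statements in Protocol Section 9.2 match a two-independent-groups formula, not the planned within-participant comparison, so the limits are 1.42 to 1.44 times too wide on the log scale

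*Protocol*

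**What the plan says.** The Synopsis describes the design: "This will be a nonrandomized, open-label, single-sequence, cross-over Phase I study in healthy participants". Tepotinib is given alone on Day 1 and with itraconazole on Day 12 to the same people.

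Protocol Section 9.4.3 specifies the primary analysis on the log scale as "A general linear model with a fixed effect for TREATMENT and a random effect for SUBJECT", giving the Day 12 versus Day 1 ratio with a 90% CI. SAP Section 16.1.3 repeats this and adds "The analysis will be repeated with both SUBJECT and TREATMENT as fixed effects". The PK analysis set (Protocol Section 9.3) takes only participants "With evaluable PK data, i.e., nonmissing values for primary endpoints", so each contributes a complete pair.

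Section 9.2 makes no hypothesis test and rests the sample size on precision. For 14 evaluable participants, a CV of 20% and an observed ratio of 1.0, it says "then the 90% CI for the ratio will be contained with 80% probability in 0.805 to 1.242". It continues: "If the observed ratio is exactly 2.0, then the corresponding limits are 1.611 to 2.484". It then concludes: "This precision is considered adequate to characterize the effect of multiple doses of itraconazole on the PK of tepotinib". It also warns that "even with a slightly smaller number of completed participants, the precision will be markedly decreased".

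Table 4 gives the same limits for three ratios, five values of N and three CVs. It labels N as the total and the CVs as within-participant. No formula is given; the footnote names only the R version.

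**The concern.** When each participant supplies both measurements, the log ratio is a mean of N within-participant differences. Its standard error is σ_w√(2/N). The printed limits are far wider than this gives. A factor near √2 is what results when the N participants are treated as two groups of N/2 while the within-participant SD is still used.

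These figures are the only quantitative support for 14 evaluable participants, and they describe a different design. Anyone who used Table 4 to judge a shortfall in evaluable participants would understate the precision actually available.

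**Working it through.** **Inputs.** N is the total number of evaluable participants (10 to 18). The within-participant CV is 10%, 15% or 20%. The CI is two-sided at 90%, so the t quantile is 0.95. The tolerance probability is 80%. All are from Section 9.2 and Table 4.

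**Formula.** With σ_w = √ln(1 + CV²), the log half-width that the CI stays within with 80% probability is

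h = t(0.95, df) × SE × √(χ²(0.80, df)/df),

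and the limits are ratio × exp(±h). At CV 20%, σ_w = √ln(1.04) = 0.1980.

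**Step 1: reproduce the printed figure.** Two independent groups of N/2: SE = σ_w√(4/N), df = N − 2. For N = 14:

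- t(0.95, 12) = 1.7823; √(15.812/12) = 1.1479; √(4/14) = 0.5345
- h = 1.7823 × 0.1980 × 0.5345 × 1.1479 = 0.2166
- exp(±0.2166) = 0.805 to 1.242, as printed; doubling the unrounded limits gives 1.611 to 2.484, also as printed.

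**Step 2: the planned comparison.** Complete pairs: SE = σ_w√(2/N), df = N − 1. For N = 14:

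- t(0.95, 13) = 1.7709; √(16.985/13) = 1.1430; √(2/14) = 0.3780
- h = 1.7709 × 0.1980 × 0.3780 × 1.1430 = 0.1515
- exp(±0.1515) = 0.859 to 1.164; at a ratio of 2.0, 1.719 to 2.327.

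**Step 3: all of Table 4 (90 limits).**

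| Formula | Limits matched to 3 decimals | Largest deviation |
|---|---|---|
| σ_w√(4/N), df N − 2 (two groups) | 90 | 0.0005 |
| σ_w√(4/N), df N − 1 | 1 | 0.038 |
| σ_w√(2/N), df N − 1 (paired) | 0 | 0.53 |
| σ_w√(2/N), df N − 2 (2×2 cross-over) | 0 | 0.51 |

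Using a 95% CI, a 90% tolerance probability or none, or σ = CV does not rescue the paired formula.

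**Step 4: size.** At N = 14 the half-widths compare as 0.2166/0.1515 = 1.43. The factor is 1.444 at N = 10 and 1.424 at N = 18, and does not depend on the CV or the ratio.

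**Step 5: what the printed limits mean under the planned analysis.** With L = ln(1.242), the probability of containment is

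P{χ²(N − 1) ≤ (N − 1) × [L/(t(0.95, N − 1)√(2/N))]²/σ_w²}.

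At a true CV of 20%:

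| N | Paired limits, ratio 1.0 | Probability that the CI lies in 0.805–1.242 |
|---|---|---|
| 14 | 0.859–1.164 | 99.9% |
| 12 | 0.846–1.182 | 98.9% |
| 10 | 0.827–1.208 | 93.4% |
| 9 | 0.816–1.226 | 87% |

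For the printed limits to be right at N = 14, the within-participant CV would have to be 28.9%. At the largest CVs in Table 3 the paired limits for N = 14 are 0.873 to 1.146 (AUC0-tlast, 17.96%) and 0.880 to 1.136 (Cmax, 16.79%).

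**Step 6: the CV summary.** The text ends the Cmax range at 16.4%, which is the 16.37% row of Table 3 rounded. The same table gives 16.79% for MS200095_0044 Part C.

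**The case against.** The strongest reply is that nothing in the trial's results depends on this. The study is descriptive, the analysis model is specified correctly in both documents, the SAP does not carry Table 4 forward, and the error is on the safe side. No rule links Table 4 to replacing participants, stopping or interpretation, and after a shortfall readers would look at the observed CI. All of that stands and limits the importance of the point. It does not make the printed probability correct.

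The formula is inferred, because the protocol does not state one. That is true, but 90 matches out of 90 leave little room for another explanation, and the printed limits are not those of the paired analysis whatever code was used.

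The wider limits might be deliberate caution, since none of the comparisons in Table 3 involves itraconazole and variability here could be larger. The text does not say so. It already allows for uncertainty by assuming 20% against observed values up to 17.96%, and it attaches a definite 80% to that assumption. It is fair, however, that the 99.9% applies only at N = 14 and a true CV of 20%.

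The statements that precision changes with N are not disputed in direction. Under the paired formula at CV 20%, the half-width grows by 10.5% from 14 to 12 participants and shrinks by 8.1% from 14 to 16, much as under the printed formula.

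**Conclusion.** The concern holds. Table 4 and both worked sentences in Section 9.2 do not describe the planned within-participant comparison. The half-widths are overstated by a factor of 1.42 to 1.44 on the log scale, mostly √2 from the standard error with a small addition from the degrees of freedom. At CV 20%, nine evaluable participants would already meet the limits that the protocol calls adequate for 14.

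This rests on complete pairs, as the PK set requires, and on the CVs being within-participant, as Table 4 labels them. The conclusion that precision is adequate survives with room to spare. The point should be fixed because the stated justification is wrong throughout and easily corrected, not because the trial is at risk.

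**What to change.** Replace Table 4 with limits from SE = σ_w√(2/N) and N − 1 degrees of freedom, and give the formula in the footnote:

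| Ratio | N | CV 10% | CV 15% | CV 20% |
|---|---|---|---|---|
| 1.000 | 10 | 0.909–1.100 | 0.867–1.153 | 0.827–1.208 |
| | 12 | 0.919–1.088 | 0.881–1.134 | 0.846–1.182 |
| | 14 | 0.927–1.079 | 0.892–1.121 | 0.859–1.164 |
| | 16 | 0.932–1.073 | 0.900–1.111 | 0.870–1.149 |
| | 18 | 0.937–1.067 | 0.907–1.102 | 0.879–1.138 |
| 2.000 | 14 | 1.853–2.159 | 1.784–2.242 | 1.719–2.327 |
| 5.000 | 14 | 4.633–5.397 | 4.461–5.604 | 4.297–5.818 |

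The remaining rows for ratios 2.000 and 5.000 are the unrounded limits for ratio 1.000 multiplied by 2 and 5.

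Restate the two sentences as 0.859 to 1.164 and 1.719 to 2.327. The sentence on fewer completers may stay; giving the limits for 12 and 10 participants beside it (0.846–1.182 and 0.827–1.208 at CV 20%) would be helpful but is optional. Bring the upper Cmax CV in the text into line with Table 3 (16.8%), after confirming the Part C entry against its source.

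The cost is one recomputed table and a few sentences. Because this is protocol text, a formal change needs ethics committee approval under Appendix 2. N, conduct and the planned analysis stay as they are.
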